**Table 3.6.9-1**

CCI [REDACTED]

[figure not shown]
CCI [REDACTED]

**Table 3.6.9-2**

CCI [REDACTED]

CCI [REDACTED]

For example, when the true response rate is 0.4 for Arm A, there is a low probability (8%) that a no-go decision will be made using this paradigm throughout the study. There is about 3.8% probability that a decision would be made before the end of the study.

## 6 VERSION HISTORY

Version	Date	Summary of Changes	Reason for Change
1.0	18Jun2018	Initial document	Initial document

## 7 APPENDIX

### 7.1 Derivation of Investigator-based RECIST 1.1 Visit Response

Guidance regarding the handling of dropouts and missing data will apply uniformly to all efficacy analyses resulting from an application of RECIST 1.1 to investigator assessed tumor measurements. For investigator reported outcomes, analyses will present outcomes reported by the investigator without consideration of missing data or censoring rules.

#### 7.1.1 Target Lesion Response

Target lesion response will be programmatically derived on the data collection instrument once RECIST 1.1 criteria are applied to the site personnel recorded target lesion measurements.

Possible values include:

- CR – Complete Response
- PR – Partial Response
- SD – Stable Disease
- PD – Progressive Disease
- NE – Non-evaluable
- NA – Not Applicable (*set value for all post-baseline disease assessments only if no target lesions are identified at baseline*)

The derivation for target lesion response is as follows (*please note the order of the algorithm below is important*):

1. If “Any Target Lesions Present” equals “No” on the *Target Lesions – Baseline* CRF, then all post-baseline “Target Lesion Response” equals “NA”.
2. Else, if “Percent Change from Nadir Sum of Diameters” is greater than or equal to 20% and the absolute increase from the nadir (defined as the “Total” for each post-baseline disease assessment minus the “Nadir Sum of Diameters”) is greater than or equal to 5 mm, then “Target Lesion Response” equals “PD”.
3. Else, if “Not Done” is selected, or “Measurement” is left blank, or “Lesion no longer Measureable” is selected and equal to “NE”, or “Lesion Intervention” is selected for any Target Lesion identified at Baseline, then “Target Lesion Response” equals “NE”.
4. Else, if “Total Non-Lymph Node” equals “0” and all Lymph Node Target Lesion “Measurements” are less than “10” individually, then “Target Lesion Response” equals “CR”.

Note: This step requires examining “Measurements” separately for Target Lesions with “Lymph Node” equal to “Yes” and “No”.

5. Else, if “Percent Change from Baseline Sum of Diameters” is less than or equal to -30%, then “Target Lesion Response” equals “PR”.
6. Else, “Target Lesion Response” equals “SD”.

If a subject has a missing tumor measurement at a disease assessment for 1 or more target lesions, the sum of diameters (longest for non-nodal lesions, short axis for nodal lesions) will be reported for the remaining target lesions. These data will be used to indicate radiologic disease progression if the sum of diameters for the observed lesions increases at least 20% from the nadir sum of diameters of all target lesions and demonstrates at least a 5 mm absolute increase from the nadir sum of diameters of all target lesions, in spite of the missing data (or if other criteria for PD are met).

### 7.1.2 Non-Target Lesion Response

Non-target lesion response will be assigned by site personnel following a qualitative overall assessment of all non-target lesions.

Possible values include:

- CR – Complete Response

- Disappearance of all non-target lesions and normalization of tumor marker level. All lymph nodes must be non-pathological in size (<10mm short axis)
- Non-CR/Non-PD – Non-Complete Response / Non-Progressive Disease
  - Persistence of one or more non-target lesion(s) and/or maintenance of tumor marker level above the normal limits
- PD – Progressive Disease
  - Unequivocal progression of existing non-target lesions.
- NE – Non-evaluable
- NA – Not Applicable (*set value for all post-baseline disease assessments only if no non-target lesions are identified at baseline*)

Though non-target lesion responses are a subjective decision made by the site personnel, certain responses may be limited depending on the non-target lesion statuses recorded. An algorithm is provided below highlighting appropriate possible non-target lesion responses based on recorded data. Reaching a red box (■) signifies having reached the only allowable non-target lesion responses based on non-target lesion statuses. Reaching a green box (■) signifies having reached the end of the algorithm and more than one possible non-target lesion response is possible from which the Investigator may choose.

1. a) If no non-target lesions are identified at baseline, all post-baseline non-target lesion responses should equal NA. ■  
b) Else, if any non-target lesions are identified at baseline, responses may be limited to CR, Non-CR/Non-PD, PD, NE (ie, responses of NA are not permitted).  
**Go to Rule 2.**
2. a) If all non-target lesions have a status are “Absent”, the responses may be limited to CR. ■  
b) Else, if at least one non-target lesion status is NOT “Absent”, the responses may be limited to Non-CR/Non-PD, PD, NE (ie, responses of CR, NA are not permitted).  
**Go to Rule 3.**
3. a) If all non-target lesions have a status of “Unequivocal Progression”, responses may be limited to PD. ■  
b) Else, if no non-target lesions have a status of “Unequivocal Progression”, responses may be limited to Non-CR/Non-PD, NE (ie, responses of CR, PD, NA are

not permitted).

**Go to Rule 4.**

c) Else, if at least one (but not all) non-target lesion has a status of “Unequivocal Progression”, the responses may be limited to Non-CR/Non-PD, PD, NE (ie, responses of CR, NA are not permitted). (*Note: No response has been eliminated as an option here.*)

**Go to Rule 5.**

4. a) If all non-target lesions have a status of “Non-evaluable” and/or “Not Done” is selected, responses may be limited to NE. ■  
b) Else, if no non-target lesions have a status of “Non-evaluable” and “Not Done” is not selected, responses may be limited to Non-CR/Non-PD (ie, responses of CR, PD, NE, NA are not permitted). ■  
c) Else, if at least one (but not all) non-target lesion has a status of “Non-evaluable” and/or “Not Done” is selected, the responses may be limited to Non-CR/Non-PD, NE (ie, responses of CR, PD, NA are not permitted). ■  
(*Note: No response has been eliminated as an option here.*)
5. a) If all non-target lesions have a status of “Non-evaluable” and/or “Not Done” is selected, responses may be limited to NE. ■  
b) Else, if no non-target lesions have a status of “Non-evaluable” and “Not Done” is not selected, responses may be limited to Non-CR/Non-PD, PD (ie, responses of CR, NE, NA are not permitted). ■  
c) Else, if at least one (but not all) non-target lesion has a status of “Non-evaluable” and/or “Not Done” is selected, the responses may be limited to Non-CR/Non-PD, PD, NE (ie, responses of CR, NA are not permitted). ■  
(*Note: No response has been eliminated as an option here.*)

If a subject has a missing tumor status at a disease assessment for 1 or more non-target lesions, radiologic disease progression will be determined if the remaining non-target lesions qualitatively demonstrate unequivocal progression (or if other criteria for PD are met).

### **7.1.3 Visit Disease Response per RECIST1.1**

Investigator visit disease response will be programmatically derived on the data collection instrument using RECIST 1.1 criteria based upon target lesion response, non-target lesion response, and new lesion data. Missing values in any of target lesion response, non-target lesion response, and new lesion data will result in the disease response not being derived.

Possible values include:

- CR – Complete Response

- PR – Partial Response
- SD – Stable Disease
- PD – Progressive Disease
- NE – Non-evaluable

Target Lesion Response	Non-Target Lesion Response	New Lesion	Derived RECIST Disease Response
CR	CR or NA	No	CR
CR	Non-CR/Non-PD or NE	No (or NE)	PR
PR	CR or Non-CR/Non-PD or NE or NA	No (or NE)	PR
SD	CR or Non-CR/Non-PD or NE or NA	No (or NE)	SD
PD	Any	Any	PD
Any	PD	Any	PD
Any	Any	Yes	PD
NE	CR or Non-CR/Non-PD or NE or NA	No	NE
NA	CR	No	CR
NA	Non-CR/Non-PD	No	SD (Non-CR/Non-PD) a
NA	NE or NA	No (or NE)	NE
NA	CR or Non-CR/Non-PD	NE	SD (Non-CR/Non-PD) a

a Per RECIST 1.1, “SD (Non-CR/Non-PD)” is preferred over “SD” for non-target disease since SD is increasingly used as endpoint for assessment of efficacy in some trials so to assign this category when no lesions can be measured is not advised.

If a subject has a missing tumor measurement at some assessment(s) for 1 or more target lesions and criteria for PD are not otherwise met, an overall response of NE will be assigned for the assessment(s).

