#### **3.4.2.1 Best Overall Response**

Best overall response is defined as the best response (in the order of CR, PR, SD, PD, and not evaluable) among all overall responses recorded from the start of treatment with investigational product until objective documentation of PD, or the last evaluable disease assessment in the absence of PD prior to the initiation of subsequent anticancer therapy or end of the study, whichever occurs first. Best overall response (BOR) will be programmatically derived based on all post-baseline disease assessments that occur prior to the initiation of subsequent anticancer treatment. BOR will be summarized with the number and percentage of subjects for the following categories: CR; PR; SD; PD; and non-evaluable (NE). At least 8 weeks [-3 days] from the first dose of investigational product must elapse without a subsequent radiological disease progression in order to assign a best overall response of SD. The definition of 54 days will allow for the protocol-defined disease assessment window of 8 weeks ( $57 \pm 3$  days) for the first post dose disease assessment.

Confirmation of CR and PR is required and must occur no fewer than 4 weeks after initial documentation of CR or PR. If CR is pending confirmation and is designated at an assessment followed by 1 or more NE assessments, and/or PR assessments such that a) the Target Lesion Response is CR and the Non-Target Lesion Response is NE, or b) the Target Lesion Response is PR due solely to an increase in one or more lymph nodes to a size  $\geq 10$  mm and the Non-Target Lesion Response is either CR or NE, CR may be confirmed thereafter. Similarly, if a PR is pending confirmation and is designated at an assessment followed by 1 or more NE and/or SD assessments, PR may be confirmed thereafter.

In general, subjects not classifiable under the RECIST 1.1 response categories due to insufficient data or early death will be classified as non-evaluable for BOR, but will be counted in the denominator of all response rate calculations. This generalization includes if a subject has missing lesion data at baseline. In this scenario, the subject will be classified as non-evaluable for BOR. If a subject is missing lesion data at a disease assessment and yet progressive disease criteria is met despite the missing data, the subject will be classified as PD.

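### SAP 7.1.3 leaves a visit with no response if a whole component is missing, with no exception for PD, contradicting its own PD rules and risking lost or late PFS and DOR events

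*SAP*

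**What the plan says.** Section 3.4.2 has the investigator-assessed RECIST response derived by program and sends the reader to Appendix 7.1 for the rules. Within that appendix, section 7.1.3 combines target response, non-target response and new-lesion data, and says: "Missing values in any of target lesion response, non-target lesion response, and new lesion data will result in the disease response not being derived".

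Other parts of the SAP treat progression differently:

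- **3.4.2.1:** where lesion data are missing at an assessment but "progressive disease criteria is met despite the missing data, the subject will be classified as PD".
- **7.1.1:** the observed target lesions can establish progression although others are unmeasured, as can any other PD criterion.
- **7.1.2, closing paragraph:** where some non-target statuses are missing, "radiologic disease progression will be determined if the remaining non-target lesions qualitatively demonstrate unequivocal progression", or if PD is met in another way.
- **7.1.3, table:** target PD, non-target PD or a new lesion each gives PD, with 'Any' in the other two columns.
- **7.1.3, closing sentence:** a missing target measurement gives NE only where PD is not otherwise met.
- **7.1.5:** PD is dated from the earliest of the target, non-target and new-lesion evidence.

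No sentence ranks these rules, and none says whether 'Any' in the table includes a missing value.

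**The concern.** In RECIST, progression in one component is enough, whatever the others show. The missing-value sentence makes the visit response depend on all three components being filled in. Read literally, a scan with measured target growth and an empty new-lesion field, or with a new lesion and an empty non-target response, yields no response.

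The derived visit response feeds BOR, DCR, DOR and PFS. If a PD visit has no response, the PFS event is missing at that scan. The subject is then censored at the last adequate progression-free assessment, or the event moves to a later scan or to death. DOR uses the same event and censoring dates. These errors lengthen PFS and DOR, and the plan describes each arm on its own, by Kaplan-Meier, without a concurrent control that might share the error.

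**Working it through.** The SAP states no figure on this point, so the check is of logic.

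**Inputs (SAP 7.1.1 to 7.1.3), adding 'missing' to each component:**
- Target response: CR, PR, SD, PD, NE, NA, missing (7 values).
- Non-target response: CR, Non-CR/Non-PD, PD, NE, NA, missing (6 values).
- New lesion: No, Yes, NE, missing (4 values).

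**Step 1. All combinations:** 7 × 6 × 4 = 168.

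**Step 2. Combinations with a PD signal, reading 'Any' to include missing.** Those without a signal number 6 × 5 × 3 = 90, so 168 − 90 = 78 give PD by the table.

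**Step 3. PD signal and nothing missing.** Complete combinations number 6 × 5 × 3 = 90. Of these, 5 × 4 × 2 = 40 have no PD signal, leaving 90 − 40 = 50.

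**Step 4. Conflicts.** 78 − 50 = 28 combinations carry a PD signal and at least one missing component. The table gives PD and the missing-value sentence gives nothing.

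| PD signal | Combinations | With a missing component |
|---|---|---|
| Target PD | 6 × 4 = 24 | 24 − 5 × 3 = 9 |
| Non-target PD | 7 × 4 = 28 | 28 − 6 × 3 = 10 |
| New lesion | 7 × 6 = 42 | 42 − 6 × 5 = 12 |

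The groups overlap in 3 combinations: 9 + 10 + 12 − 3 = 28.

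**Step 5. Allowing for 7.1.1.** That section tests for PD first and only then codes a blank target measurement as NE, so the target component should rarely be missing. If it never is, the combinations with a PD signal number 6 × 6 × 4 − 5 × 5 × 3 = 144 − 75 = 69. Removing the 50 complete ones leaves 19 conflicts, all from a blank non-target response or new-lesion field.

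**Step 6. Effect of giving PD precedence.** All 28 become PD. Coding the missing component as NE also gives PD in all 28, because NE never blocks PD in the table.

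**Step 7. Size per affected subject.** Section 3.4.2.4 equates two scheduled assessments with 16 weeks, so one interval is 8 weeks. If the next scan shows PD, the delay is 56 / (365.25 / 12) = 56 / 30.44 = 1.84 months. If no later scan is done and the subject is alive, the event becomes a censored observation. At the planned maximum of about 46 (Arm A) and 52 (Arm B), one affected subject is 1/46 = 2.2% or 1/52 = 1.9% of an arm.

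**Rule 5a of 7.1.2.** Rule 5 is reached only through Rule 3c, where at least one non-target lesion, but not all, has Unequivocal Progression. 'All lesions Non-evaluable' therefore cannot hold there. If 'Not Done' in 5a stands alone, it forces NE despite a progressing lesion, and the mention of 'Not Done' in 5c can never be reached. If 'all' governs both conditions, 5a cannot fire, and the case passes to 5b or 5c, which both permit PD.

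**The case against.** The strongest reply is that the sentence stands alone against five sections or rules that favour PD, so a sensible programmer would assign PD. The sentence also follows one about derivation on the data collection instrument, and could describe only when a CRF field fills itself. The first part has weight: most of the text does favour PD. The second is not conclusive, because 3.4.2 makes Appendix 7.1 the derivation for the efficacy analysis. Neither supplies the missing order of precedence.

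Four stronger readings are tempting, and the SAP does not support them:

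- *Any blank field loses the progression.* It does not. A blank target measurement is coded NE after the PD test, a non-target 'Not Done' can be answered NE, and NE beside a PD component still gives PD. Only a wholly missing component-level value triggers the sentence.
- *The SAP settles that such PD is lost.* It does not; it says two incompatible things.
- *Rule 5a plainly contradicts the end of 7.1.2.* That holds on one of two readings only, and the closing paragraph of 7.1.2 favours the other.
- *A number of lost events per arm can be given.* The SAP states neither an expected PFS event count nor a rate of blank components. Whether blanks would survive data queries cannot be seen.

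It is also fair to say that PFS and DOR are secondary and are described without a test.

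**Conclusion.** The contradiction is real and can be verified from the SAP text alone. Section 7.1.3 contains an unqualified rule that, if followed when a component-level value is blank, removes or delays a progression that the rest of the SAP would count. For each affected subject, PFS or DOR is censored early or dated late, by about 1.8 months if the next 8-week scan shows PD. DCR may rise, because the SD criterion turns on the absence of radiological progression. If visits without a derived response are counted as missed, which the SAP leaves open, two in a row could also cause a later PD or death to be censored.

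The primary endpoint is barely touched. A BOR of PD and one of NE are both non-responses, and the ORR denominator is fixed. ORR could change only if a response confirmed after the dropped PD visit were counted, so the effect is negligible.

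The 28 and 19 conflicts measure how far the rules disagree, not how often this will happen; the frequency cannot be estimated from the SAP. The case for changing the text is that two programmers following the same plan could produce different event dates.

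**What to change.** In 7.1.3, replace the unqualified sentence with a rule of this form: *PD in any available component (target PD, non-target PD or a new lesion) gives a visit response of PD, regardless of missing values in the other components; the response is left underived for a missing component only when no component shows PD.* A table note that 'Any' includes missing would make the same point where programmers will look. Nothing more is needed to remove the conflict; recoding the remaining incomplete visits as NE would be a separate choice.

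As a minor clarification, reword Rule 5a of 7.1.2 so that 'Not Done' cannot force NE when a non-target lesion has Unequivocal Progression.

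The cost is two short edits to the SAP appendix and a small change to the derivation program. Data collection and sample size are unaffected.

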#### 7.1.4 Locoregional therapy

Any subject receiving locoregional therapy, including surgery, while on study that directly affects one or more of the target lesions selected at baseline and/or new lesions included in tumor burden will be identified. A subject with a subsequent response or SD/irSD will be considered to be non-evaluable at all disease assessments that occur on or after the date of locoregional therapy. Otherwise, the subject will be assessed ignoring the locoregional therapy.

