#### **3.4.2.3 Duration of Response**

Duration of response (DOR) is defined as the time from the first documentation of a subsequently confirmed objective response until the first documentation of disease progression or death due to any cause, whichever occurs first regardless of whether the subject receives subsequent anticancer therapy prior to progression. For subjects who are alive and progression-free at the time of data cut-off for analysis, DoR will be censored at the last tumor assessment date. Only subjects who have achieved objective response (confirmed CR or confirmed PR) will be evaluated for DOR. DOR is defined in months as follows:

$DOR \text{ (months)} = (\text{Date of PD/death or censoring} - \text{Date of first confirmed disease response} + 1) / (365.25/12),$

The date of PD/death or censoring is the same as defined for PFS. The median DOR and its 95% CI will be estimated using the Kaplan-Meier method.

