#### **3.4.2.4 Progression-free Survival**

Progression-free survival (PFS) is defined as the time from the first dose of investigational product until the first documentation of a disease progression or death due to any cause, whichever occurs first, regardless of whether the subject receives subsequent anticancer treatment prior to progression. Patients who have no documented progression and are still alive at the time of analysis will be censored at the time of the latest date of assessment from their last evaluable RECIST 1.1 assessment. PFS is defined in months as follows:

$PFS \text{ (months)} = (\text{Date of PD/death or censoring} - \text{Date of the first dose of investigational product} + 1) / (365.25/12),$

The censoring guidance and the date of PD/death or censoring are given in the table below. The number and percentage of patients experiencing a PFS event and Kaplan-Meier plots of PFS will be presented by treatment group. The median PFS and its 95% CI will be estimated using the Kaplan-Meier method. The proportion of subjects progression free and alive at time points of interest months (such as 3 months and 6 months) and associated 95% CI will be estimated using the Kaplan-Meier method.

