**Table 3.4.2-1 Summary of Censoring Guidelines for PFS**

Situation	Date of PD/Death or Censoring	PFS Outcome
Documented Progressive Disease (PD) or death	Date of earliest sign of PD or death, whichever comes first	Event (unless the censoring rule specified below)
Death or PD immediately after $\geq 2$ consecutive missed or non-evaluable disease assessments as per the protocol specified assessment schedule	Date of last progression-free disease assessment prior to missed or non-evaluable assessments, or the first dose of investigational product, whichever occurred last	Censored
No PD or death at time of analysis or lost to follow-up	Date of last adequate progression-free disease assessment	Censored
No tumor assessment at baseline and no evidence of PD at first post-baseline disease assessment OR No tumor assessment post-first dose, and no death prior to second scheduled post-baseline disease assessment	Date of the first dose of investigational product	Censored

PD = progressive disease; PFS = progression-free survival

Subjects having missing lesion data at baseline or no disease assessments post-first dose of investigational product will have PFS censored at the date of the first dose of investigational product unless the subject dies prior to the second scheduled post-baseline disease assessment in which case the death date will qualify as a PFS event.

If a subject has two or more consecutive completely missed or non-evaluable assessments followed immediately by death or an assessment showing radiologic disease progression, then the subject will be censored for PFS. PFS will be censored at the date of the first dose of investigational product or the last progression-free disease assessment prior to the missed or non-evaluable assessments, whichever occurred last.

If a subject has two or more consecutive missed or non-evaluable assessments followed by an assessment showing no radiologic disease progression, then the assumption will be that the subject did not progress during the missed or non-evaluable assessments. Two or more consecutive assessments is defined as  $\geq 16$  weeks plus 6 days (two disease assessments as per protocol plus a 6 days visit window to allow for a late assessment) after the last evaluable post-baseline disease assessment.

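### The locoregional-therapy rules make later non-progressing scans non-evaluable, so PFS and DOR can censor an observed progression or late death back to before the therapy

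*SAP*

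**What the plan says.** Section 7.1.4 covers on-study local therapy, including surgery, that directly affects a baseline target lesion. It is conditional: a subject who later shows response or SD/irSD is "considered to be non-evaluable at all disease assessments that occur on or after the date of locoregional therapy". For anyone else, "Otherwise, the subject will be assessed ignoring the locoregional therapy".

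Section 7.1.1 reaches a similar place by another route. Its ordered algorithm tests target-lesion PD at step 2 and only then, at step 3, sets the target response to NE if Lesion Intervention is ticked for any baseline target lesion. The Section 7.1.3 table turns a target response of NE into a visit response of NE, unless non-target lesions progress or a new lesion appears; either of those gives PD.

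Section 3.4.2.4 defines PFS as time to first PD or death, "whichever occurs first, regardless of whether the subject receives subsequent anticancer treatment prior to progression". Section 3.4.2.3 defines DOR in the same spirit and adds: "The date of PD/death or censoring is the same as defined for PFS".

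Table 3.4.2-1 and its text censor a subject who has "two or more consecutive completely missed or non-evaluable assessments followed immediately by death or an assessment showing radiologic disease progression". The censoring date is the last progression-free assessment before that run (or first dose, if later). Two or more assessments means at least 16 weeks plus 6 days after the last evaluable one. Visits that are NE only because of local therapy are not exempted.

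Sections 3.4.3 and 7.1 apply the missing-data guidance uniformly to all RECIST-derived efficacy analyses, so Section 7.1.4 cannot be read as limited to ORR.

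**The concern.** Setting a response or SD to NE after a target lesion has been treated locally is sensible for response endpoints, because the shrinkage may be due to the local therapy. Carried into PFS and DOR, the same label does something else. Scans that were done and showed no progression are treated like missed scans, and a PD or death later seen in that subject is removed and replaced by censoring before the therapy.

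Who receives local therapy is decided after baseline and is plausibly linked to prognosis. Affected subjects must also have had SD or response afterwards. Kaplan-Meier estimation assumes that censoring carries no information about the outcome, and here it probably does. PFS and DOR are descriptive secondary endpoints, but in a single-arm cohort they are read at face value.

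The rules are also open to two readings. Literally, Section 7.1.4 blanks all later assessments, including one showing PD. Sections 7.1.1 and 7.1.3 let PD stand after an intervention. Two programmers could derive different PFS dates from the same data.

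**Working it through.** **1. The window.** Two 8-week intervals plus two 3-day allowances: 2 × 56 + 2 × 3 = 118 days. The SAP's figure is 16 × 7 + 6 = 118 days. It reproduces.

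**2. Rules applied to example subjects.** Day 0 is the last evaluable assessment (SD). Local therapy to a target lesion follows shortly after. Scans fall on days 56, 112 and 168; the 8-week interval is inferred from the SAP equating two assessments with 16 weeks. The subject-level reading blanks every later assessment once a response or SD has occurred. The assessment-level reading blanks only the non-progressing ones, as Section 7.1.1 step 3 with Section 7.1.3 also does.

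| After therapy | Therapy ignored | Subject-level | Assessment-level |
|---|---|---|---|
| PD at first scan | event, day 56 | event, day 56 | event, day 56 |
| SD, PD | event, day 112 | censored, day 0 | event, day 112 |
| SD, SD, PD | event, day 168 | censored, day 0 | censored, day 0 |
| SD, death on day 90 | event, day 90 | event, day 90 | event, day 90 |
| SD, SD, death on day 140 | event, day 140 | censored, day 0 | censored, day 0 |

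For PD, the subject-level loss arises because the PD visit itself becomes NE. The assessment-level loss arises through the two-missed rule. Deaths are lost through the two-missed rule on both readings.

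**3. In calendar terms.** SD at weeks 8 and 16, therapy at week 20, no progression at weeks 24 and 32, new-lesion PD at week 40. The gap is (40 − 16) × 7 = 168 days, which exceeds 118, so the subject is censored at week 16 on either reading. With the SAP formula (days from first dose + 1, divided by 365.25/12 = 30.4375):
- PFS definition: (280 + 1)/30.4375 = 9.2 months, event.
- Combined rules: (112 + 1)/30.4375 = 3.7 months, censored.

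**4. Is Section 7.1.4 the only source?** No. Delete it from the example: step 3 of Section 7.1.1 still makes the target response NE at weeks 24 and 32, Section 7.1.3 makes both visits NE, and Table 3.4.2-1 still censors at week 16.

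**5. How many subjects?** The SAP gives no frequency. As an assumption, 1 to 5 affected subjects would be 1/46 = 2.2% to 5/46 = 10.9% of Arm A, or 1/52 = 1.9% to 5/52 = 9.6% of Arm B.

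**6. Effect on the median.** Simulation under assumptions not taken from the SAP: 46 subjects, exponential PFS with median 6 months, 8-week scans, 5 subjects with PD at scan 4 or later recoded as censored three scans earlier, 3,000 runs. The mean Kaplan-Meier median changed by about −0.25 to +0.1 months. The sign depended on how the median is read when the curve sits exactly at 0.5, and the median was unchanged in roughly 80% to 93% of runs. This supports no directional claim.

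**The case against.** The strongest reply is that Table 3.4.2-1 already qualifies the definition: PD or death is an "Event (unless the censoring rule specified below" applies. Any PFS definition paired with a two-missed rule carries that tension. The SAP also never says that on-study local therapy is subsequent anticancer treatment. If it is not, the clause counting events despite such treatment is not engaged. If it is, Sections 3.4.1.1 and 3.4.2.1 already cut ORR and BOR at that point. Finally, progression is hard to time once a target lesion has been treated, so censoring at the last evaluable scan is a defensible convention.

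Much of this stands. The problem is an unintended interaction and an ambiguity, not a flat contradiction. But the undefined term does not rescue the text. If local therapy is subsequent treatment, Section 7.1.4 adds little for response and acts mainly on PFS and DOR, against their definitions. If it is not, PD after a switch to new systemic therapy counts while PD after SD following local therapy can be lost, with no reason given. And if censoring at local therapy were intended, Table 3.4.2-1 should say so; it does not.

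A reader might infer that every assessment after local therapy becomes non-evaluable and that all later progressions and deaths are lost. The documents do not support this. The rule needs a later response or SD; PD at the first later scan counts; a death under 118 days after the last evaluable scan stays an event.

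**Conclusion.** The point holds for a defined group: subjects with SD or response after on-study local therapy to a baseline target lesion. For them, PD or death at least 118 days after the last evaluable assessment is censored back to before the therapy on either reading of Section 7.1.4. On the literal reading, any later PD visit is erased as well, against the PD-first order in Section 7.1.1 and the new-lesion row in Section 7.1.3.

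The reach is limited to PFS and DOR. OS is untouched, and so is the primary ORR as far as this censoring is concerned. Size per subject can be large (9.2 months as an event against 3.7 months censored in the example), but the size per cohort cannot be given: the number affected is not in the SAP, and step 6 yields no stable shift in the median. It would be wrong to infer a particular bias in the median or its direction. That the censoring is informative is a judgement from how subjects enter the group, not a measured quantity. The assumptions are 8-week scans throughout and therapy given soon after an evaluable scan.

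**What to change.** Amend the wording in three places:

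1. Section 7.1.4: state that only the response or SD assessments after local therapy are set to NE, and only for BOR, ORR and DCR.
2. Sections 3.4.2.3 and 3.4.2.4: state that after local therapy a PD (target-lesion criteria met in spite of the intervention, non-target progression or a new lesion) or a death is an event on its own date.
3. Table 3.4.2-1: state that an assessment that was performed but is NE solely because of Section 7.1.4 or Lesion Intervention in Section 7.1.1 does not count as missed or non-evaluable.

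The third item is essential, since step 4 shows that limiting Section 7.1.4 alone leaves the example unchanged. A sentence saying whether on-study local therapy is subsequent anticancer treatment would remove the remaining doubt.

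The cost is a few sentences and a small derivation change. The downside is that PD may be dated after a period in which the treated lesion could not be assessed; a sensitivity analysis censoring at local therapy would show how much that matters. The irSD term in Section 7.1.4 does not fit a RECIST 1.1 appendix, but that is editorial only.
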